2.1. Specific Aims

Aim 1: Determine the effectiveness of economic incentives contingent on point-of-care (POC) urine ethyl glucuronide (EtG) <300 ng/mL (Arms 2 & 4) versus no alcohol incentives (Arms 1 & 3) to reduce heavy drinking over 6 months, among HIV/TB co-infected adult drinkers receiving IPT. We will randomize participants to low-cost escalating prize incentives for EtG negative urine tests at IPT refill visits (Arms 2+4), versus no incentives (Arms 1+3).

- Hypothesis: Incentives will be more effective in promoting decreased alcohol use during IPT versus the control, resulting in less hepatotoxicity and greater IPT adherence in the intervention versus the control group.
- Outcomes: Primary: Non-heavy drinking determined by self-report (Alcohol Use Disorders Identification Test – Consumption [AUDIT-C], prior 3 months, negative) *and* phosphatidylethanol (PEth) <35 ng/mL at three *and* six months. Secondary: IPT adherence and hepatotoxicity.

Aim 2: Determine the effectiveness of economic incentives contingent on POC (IsoScreen) INH urine positive tests (Arms 3 & 4) versus no INH incentives (Arms 1 & 2) on INH adherence among HIV/TB co-infected adult drinkers. We will randomize participants to low-cost escalating prize incentives for INH positive urine tests at IPT refill visits (Arms 3+4), versus no incentives (Arms 1+2).

- Hypothesis: The incentive strategy will result in greater INH adherence versus the control.
- Outcomes: Primary: INH adherence measured as >90% pill-taking days by medication event monitoring system (MEMS) cap opening over six months. Secondary: INH concentration in hair at 3 and 6 months.

Aim 3: Assess the impact of economic incentives on HIV virologic suppression and explore their mechanisms of action, six months after trial completion. We will follow all study participants for six months after trial completion.

a) **Assess the impact of the 3 separate incentive interventions (Arms 2,3,4) vs. no incentives (Arm 1) on HIV virologic suppression.**

- Hypothesis: The intervention arms will be associated with greater viral suppression versus control.
- Outcomes: Primary: The proportion with undetectable HIV viral load six months post-IPT completion. Secondary: Active TB rates six months after IPT completion.

b) **Explore the mechanisms that may drive the economic incentives to increase virologic suppression.**
Potential mediators will be reductions in alcohol use and level of IPT adherence.

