Heavy drinking is common among HIV-infected persons and heavy drinkers are at increased risk for active TB and poorer TB treatment outcomes. In several studies of persons in HIV care in sub-Saharan Africa (SSA), a median of 25% of persons self-reported heavy drinking,¹³⁻¹⁸ with heavy drinking defined as exceeding recommended limits, e.g. via the NIAAA drinking limits (women: >7 drinks/week or >3 drinks/occasion; men:>14 drinks/week or >4 drinks/occasion) or via the AUDIT-C.^{19,20} Heavy alcohol consumption is an established risk factor for HIV,^{21,22} and for TB infection via increased immunosuppression and increased time spent in settings where TB is prevalent.¹ The risk of active TB is increased 3-fold among heavy drinkers compared to non-drinkers,^{1,23-25} and heavy drinkers with TB are more likely to have sputum smear positive disease, slower presentation to care, worse TB treatment response, and higher mortality while on TB treatment.^{1,26} Thus, HIV-infected drinkers are at high risk of morbidity and mortality due to active TB disease and should be a priority for TB preventive treatment.

Interventions are needed to reduce the risk of INH-related toxicity among HIV/TB co-infected drinkers. INH is metabolized by the liver, and the rate of Grade 3/4 (serious) hepatotoxicity due to INH ranges from 0.1-4.0% of all patients.²⁷ Most INH-associated hepatotoxicity is reversible by stopping therapy, but liver injury can, rarely, lead to liver transplantation or death, with mortality rates of 0.05-0.10%.²⁸ Alcohol users are considered at increased risk for INH-related hepatotoxicity. In the U.S., alcohol users with latent TB infection may be given IPT, with liver enzyme monitoring recommended to improve safety.²⁹ However, the WHO lists “regular and heavy alcohol consumption” as a contraindication to IPT in resource-limited settings, given the challenges of clinical oversight and liver enzyme monitoring.¹² It is therefore important to attempt to reduce the risk of toxicity by intervening to reduce drinking. In a research setting, comprehensive monitoring is feasible, thus INH can safely be given to drinkers (see Safety Considerations) while studying interventions to optimize IPT. Thus, Aim 1 of this study is to conduct a trial to determine whether an incentive-based intervention can reduce drinking in HIV/TB co-infected heavy drinkers receiving 6 months of INH to reduce the risk of hepatotoxicity.

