5.5. Study visits

As previously described, eligibility will be a two-stage process in order to determine drinking status, TST status, and rule out active TB and liver enzyme elevations. Baseline visits will include collection of tracking information, a baseline survey (Table 2), blood draw, and repeat liver enzyme testing if it has been longer than one month from the screening tests.

[figure not shown]
Visits for INH refills and assessments for toxicity (assessment of side effects and liver enzyme testing) will occur at week 2 and months 1 through 6 for all study participants. Urine will be collected and prizes administered as described above for Arms 2, 3, and 4. Hair collection will occur at 3 and 6 months c at the time of the INH discontinuation if outside of the 3- and 6-month time point for all study participants (see below). Follow-up interviews and blood collection will occur at months 3, 6, and 12 (Table 2). Screening for symptoms of active TB, and sputum testing and chest X-ray if symptoms are reported, will occur at every follow-up visit.

Arms 2-4 only: Urine test(s) and prize(s)
↓
Month 12: Study survey, Blood draw (PEth, VL)

Retention: High retention (90% at six months, 85% at one year) will be maintained as in our prior studies using follow-up phone calls, alerts when patients come to their home clinic, and home visits when needed. To encourage high retention, participants in all study arms, including control, will receive travel reimbursements (low-value unconditional cash transfers) of up to US\$5 for attending study visits (see Figure 3).

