Hepatotoxicity. A secondary outcome will be treatment discontinuation due to a Grade 3/4 hepatotoxicity at any time during the treatment period. Grade 3/4 hepatotoxicity is defined as in previous trials³ as ALT or ALT $>3-5$ ULN and symptoms (nausea, vomiting, jaundice, or fatigue) or ALT or AST >5 ULN, regardless of symptoms. Study clinicians, blinded to intervention arm, will determine treatment discontinuation.

HIV viral suppression. The primary outcome for Aim 3 will be HIV viral suppression 12 months post-enrollment. We will also examine viral load six months post-enrollment as a secondary outcome for Aim 3.

Active TB. A secondary outcome for Aim 3 will be active TB at any time during the 12 months post-enrollment. Active TB will be defined as confirmed (if Xpert MTB/RIF assay positive) or suspected (based on chest x-ray findings or response to anti-TB treatment in symptomatic, Xpert assay negative persons).

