5.9.1. Aim 1 analyses

The primary analysis will use multiple logistic regression models where the main independent variable is a binary variable representing assignment to economic incentives for non-heavy alcohol use (yes vs. no). The model will additionally control for assignment to incentives for IPT adherence (yes vs. no) and randomization stratification factors (i.e., gender and study cohort), to improve efficiency, and potential confounders not balanced on randomization.

The secondary outcome of treatment discontinuation due to hepatotoxicity will be analyzed using the same approach. However, if the number of hepatotoxicity events is sparse, the penalized likelihood method will be used.¹⁸¹ We will conduct similar analyses using INH adherence >90% as the outcome to evaluate whether there is an impact of economic incentives for decreasing alcohol use on IPT adherence. We will use linear regression models to examine continuous secondary outcome variables such as PEth levels, and will explore transformations for variables that are not normally distributed. If an appropriate transformation is not identified, a median regression model will be used.^{182,183}

Statistical power: With 680 participants enrolled, we anticipate 612 participants will complete both 3- and 6-month follow-up (i.e. 10% loss to follow-up). Assuming 2-sided tests, with an overall significance level of 0.05, and that 15% of controls will have no heavy drinking based on our prior data, the proposed study has 80% power to detect an absolute difference of 10% (i.e. 25% vs. 15% in the intervention and control arms, respectively) in the proportions with no heavy drinking using a chi-square test with continuity correction.

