Figure 1. Schematic of study design and aims of the Drinkers' Intervention to Prevent TB (DIPT) trial

Objectives

The DIPT trial is designed to achieve three aims. Aim 1: To determine the effectiveness of financial incentives contingent on low alcohol use (Arms 2 and 4) versus no alcohol incentives (Arms 1 and 3) to reduce heavy drinking during INH preventive therapy. The hypothesis for Aim 1 is that participants receiving incentives for negative urine EtG testing will have lower alcohol use, determined via a medium-term alcohol biomarker during INH, compared to participants receiving no alcohol incentives. Aim 2: To determine the effectiveness of financial incentives contingent on high INH adherence (Arms 3 and 4) versus no INH adherence incentives (Arms 1 and 2) to increase INH adherence during INH preventive therapy. The hypothesis for Aim 2 is that participants receiving incentives for positive POC IsoScreen testing will have better adherence to INH, determined via objective monitoring, than participants receiving no INH adherence incentives. Aim 3: To determine the effectiveness of financial incentives (Arms 2, 3, and 4) versus no financial incentives (Arm 1) on HIV virological suppression after completing their INH preventive therapy. The hypothesis for Aim 3 is that participants receiving financial incentives have higher rates of HIV virological suppression six months after INH completion.

Primary outcomes

The study has two primary outcomes. The primary outcome for Aim 1 (i.e., to estimate the effect of incentives contingent on negative urine EtG tests) is no heavy alcohol consumption over the six months of INH preventive therapy, a binary variable. This is defined as a composite outcome of both PEth <35 ng/mL and negative AUDIT-C score at both the 3- and 6-month visits. We will use standard AUDIT-C cutoffs (≥ 3 for women and ≥ 4 for men) to define heavy drinking.

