The primary outcome for Aim 2 (i.e., to estimate the effect of incentives contingent on a positive IsoScreen test) will be INH adherence measured as >90% pill-taking days by MEMS cap opening during the six-month course of INH or the time prescribed for those who were instructed to discontinue INH, a binary variable. The participants were given up to 9 months to complete a 6-month (180-pill) INH preventive therapy course. Therefore, MEMS adherence is defined as the number of pill bottle openings (no more than 1 per day counted) within a 270-day window divided by the number of prescribed doses (180, unless the participant discontinued the medication).

The outcome for Aim 3 is treated as a secondary outcome (see below).

Secondary outcomes

The secondary outcome for Aim 1 is PEth as a continuous variable measured at the 6-month visit.

The secondary outcome for Aim 2 is MEMS-measured adherence as a continuous variable (defined as the proportion of days with a bottle opening out of number of days prescribed within 9 months of randomization).

The outcome of Aim 3 is HIV virological suppression defined as an undetectable plasma HIV viral load at the 12-month visit (a binary variable). Another secondary outcome for Aim 3 will be HIV virological suppression at the 6-month visit (a binary variable).

Another secondary outcome is INH preventive therapy discontinuation due to grade 3 or grade 4 hepatotoxicity at any time while receiving INH (a binary outcome). Grade 3 hepatotoxicity was defined as AST or ALT ≥ 5 ULN or based on symptoms that met pre-specified Grade 3 criteria for hepatotoxicity. Grade 4 hepatotoxicity was defined as AST or ALT ≥ 10 ULN or based on symptoms that met pre-specified Grade 4 criteria for hepatotoxicity.

Finally, active TB during the 12 months of follow-up (a binary outcome) is also a secondary outcome. Active TB is defined as confirmed (if Xpert MTB/RIF assay positive) or suspected (based on chest x-ray findings or response to anti-TB treatment in a symptomatic and Xpert assay negative person).

Descriptive statistics

We will report the distribution of baseline covariates overall and by randomization arm. For continuous variables, we will provide the median, mean, standard deviation, 0th, 25th, 50th, 75th, and 100th percentiles. For categorical variables, we will provide frequencies and proportions. Differences between arms will not be evaluated based on statistical significance.

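### The protocol hypothesises less hepatotoxicity, but the only between-arm liver comparison is a rare discontinuation event with low power; the repeated ALT/AST data enter only through grade cut-offs

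*SAP*

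**What the plan says.** Protocol section 2.1 states that the alcohol incentives will reduce drinking, "resulting in less hepatotoxicity and greater IPT adherence in the intervention versus the control group". Sections 3 and 5.7.1 also give a lower risk of INH toxicity as the reason for Aim 1. The SAP (Objectives) narrows the Aim 1 hypothesis to drinking: "participants receiving incentives for negative urine EtG testing will have lower alcohol use, determined via a medium-term alcohol biomarker during INH".

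Both documents keep one liver outcome. Protocol section 5.7.1: "A secondary outcome will be treatment discontinuation due to a Grade 3/4 hepatotoxicity at any time during the treatment period". SAP, Secondary outcomes: "INH preventive therapy discontinuation due to grade 3 or grade 4 hepatotoxicity at any time while receiving INH (a binary outcome").

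The planned analyses differ. Protocol section 5.9.1 uses the Aim 1 factorial model, with penalised likelihood if events are sparse. The SAP (Analyses of the secondary outcomes) uses three pairwise comparisons with Arm 1 and names no sparse-event method. Hepatotoxicity is the only binary secondary outcome that the SAP takes out of the factorial analysis.

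On frequency, protocol section 3 says that "the rate of Grade 3/4 (serious) hepatotoxicity due to INH ranges from 0.1-4.0% of all patients", and adds: "Alcohol users are considered at increased risk for INH-related hepatotoxicity".

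On measurement, protocol section 5.5 says that assessments for toxicity (side effects and "liver enzyme testing) will occur at week 2 and months 1 through 6 for all study participants". Table 2 adds a test at eligibility. Neither document lists an ALT or AST level, peak, change or lower-grade elevation as a secondary or exploratory outcome.

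**The concern.** The trial's case for paying heavy drinkers to drink less while on INH rests partly on liver safety. Better INH adherence in heavy drinkers might also affect the liver, so both factorial margins matter. If the only comparison is a rare yes/no event, a null result will say little about the protocol's hypothesis. The SAP's pairwise tests use half the sample each. They also omit the contrast of Arms 2+4 with Arms 1+3, which addresses that hypothesis directly, and the contrast of Arms 3+4 with Arms 1+2, which addresses the adherence incentives. Meanwhile a laboratory measure taken up to seven times on treatment in everyone is reduced to whether it crossed a high threshold.

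**Working it through.** **Inputs.** 680 randomised 1:1:1:1 (protocol 5.3), so 340 per factorial margin and 170 per arm. For evaluable numbers: "With 680 participants enrolled, we anticipate 612 participants will complete both 3- and 6-month follow-up (i.e. 10% loss to follow-up"), so 306 per margin. Two-sided alpha is 0.05 (protocol 5.9.1; the SAP uses 0.05 for each secondary outcome). The event rate is 0.1% to 4.0% (protocol 3). The documents give no target liver effect, so a halving is assumed here.

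**Formula.** With p̄ the mean of p1 and p2, and d = |p1 − p2|:

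power = Φ{[d − 1.96·√(2p̄(1 − p̄)/n)] / √[(p1(1 − p1) + p2(1 − p2))/n]}

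For the continuity correction, replace n by (n − 1/d)²/n.

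**Calibration on the plan's own figures.** No power is stated for the liver outcome. The nearest figure is Aim 1: 80% for 25% v 15% with 612 evaluable. At 306 v 306 the corrected formula gives 85.1%. At 80% power the smallest detectable differences are 9.3 points (Aim 1, stated 10), 11.6 (Aim 2, stated 12) and 17.0 (Aim 3a, stated 17; 80.1% at that difference). The stated Aim 1 and Aim 2 figures therefore look rounded up, which is conservative and not an error.

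**Expected events.** If one rate applied to all 680: 0.001 × 680 = 0.7, to 0.04 × 680 = 27. At 4% v 2%: 340 × 0.04 + 340 × 0.02 = 20.4.

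**Power at 4% v 2%.**
- 340 v 340: (0.02 − 1.96 × 0.01308)/0.01306 = −0.43, so power is 33.3%.
- 170 v 170: (0.02 − 1.96 × 0.01850)/0.01847 = −0.88, so power is 18.9%.

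**Power for a halving, by control rate** (exact Fisher power in brackets):

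| Control rate | Factorial, 340 v 340 | SAP pairwise, 170 v 170 |
|---|---|---|
| 1% | 11.4% (3.1%) | 7.7% (0.3%) |
| 2% | 18.7% (10.7%) | 11.5% (3.1%) |
| 4% | 33.3% (26.5%) | 18.9% (10.5%) |
| 6% | 47.1% (40.6%) | 26.5% (18.1%) |
| 8% | 59.4% (53.5%) | 34.1% (26.2%) |
| 10% | 69.8% (65.2%) | 41.7% (33.9%) |

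Rates above 4% lie outside the cited range and are shown because drinkers may be at higher risk. With the uncorrected formula, 80% power needs a control rate of about 12.5% (340 v 340) or 22.8% (170 v 170). At a 4% control rate it needs about 1,141 per side (1,239 with continuity correction).

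**A continuous enzyme measure.** The difference detectable with 80% power is (1.96 + 0.84)·√(2/n) in SD units: 0.21 at n = 340, 0.23 at n = 306 and 0.30 at n = 170. Converting this to ALT needs an SD that the documents do not give. If the baseline-adjusted SD of log ALT is assumed to be 0.4 to 0.7, the detectable ratio of geometric means at 306 v 306 is exp(2.80 × 0.4 × √(2/306)) = 1.09 to exp(2.80 × 0.7 × √(2/306)) = 1.17, a 9% to 17% difference.

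**The case against.** Low power for a rare secondary safety outcome is common and is not in itself an error. That is fair, and it is why this is an improvement to the plan and not a flaw in its primary analyses. Several stronger readings are tempting and are not supported.

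- **That power is at most one-third.** The 4% is a rate for all patients, and the protocol says drinkers are considered at higher risk. At 6% to 10% the factorial power for a halving is 47% to 70%. The halving is also an assumption.
- **That the analysis could not reveal harm.** A doubling from 4% to 8% has 59% power at 340 v 340 and 34% at 170 v 170. That is limited, but not negligible.
- **That the enzymes are never compared.** They enter through the Grade 3/4 thresholds. The data and safety monitoring board, with an added hepatologist, also reviews safety data every six months (protocol 6.4), although that is monitoring and not a planned between-arm estimate.
- **That unblinded staff decide the outcome.** Research assistants know the arm and record side effects, but physicians blinded to arm decide on grade and discontinuation (protocol 5.7.1, 6.2), and high enzymes qualify without symptoms.
- **That the SAP fails its own hypothesis.** The liver hypothesis is stated in the protocol only.

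Two objections to an enzyme analysis stand and shape the fix. A peak value tends to rise with the number of tests, and that number may differ by arm through missed visits, stopping INH and the 2020 pause. Also, entry requires ALT and AST below twice the upper limit of normal (ULN), so a modest shift in the mean may stay far from serious toxicity. The enzymes are a surrogate and cannot replace the discontinuation outcome.

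**Conclusion.** The point holds as an inexpensive improvement. At the highest cited rate, the liver comparison has about 33% power for a halving under the protocol's factorial contrast and about 19% under the SAP's pairwise tests. Low power does not depend on 4% being a ceiling: under a halving, power stays below 80% unless the control rate exceeds about 12.5% (factorial) or 23% (pairwise). Existing ALT/AST data could detect about 0.23 SD at 306 v 306, a figure that needs no outside input; the 9% to 17% translation depends on the assumed SD. What such a shift would mean for serious hepatotoxicity is not established in the documents. The move from factorial to pairwise testing, and the loss of the sparse-event method, are separate weaknesses in the SAP's handling of the same outcome.

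**What to change.** 1. **Add a supportive secondary or exploratory liver analysis.** Model log on-treatment ALT, and separately AST, as a multiple of ULN, by linear regression on both incentive factors, gender, site and the screening value. Report geometric mean ratios with 95% confidence intervals for each factorial margin.
2. **Guard against unequal numbers of tests.** Use the mean on-treatment level or a repeated-measures model over scheduled visits, with the peak as a sensitivity analysis.
3. **Report counts** of ALT or AST above 3 and above 5 times ULN by arm.
4. **Keep the discontinuation outcome as pre-specified**, but analyse it with the factorial contrast and with penalised likelihood if events are sparse, as in protocol 5.9.1.
5. **Label the enzyme analysis supportive**, and post hoc if arm-level data have already been seen.

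The cost is a paragraph in the SAP and one main model per enzyme, plus the peak sensitivity analysis, with no new data. The downside is a surrogate measure and a few more secondary comparisons without multiplicity adjustment.
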